Visit window (days) ^{a)}	±0	±3	±3	±7	±7	±7	±7	±7	±7							
Vital signs	X	X	X	X	X	X	X	X	X							8.2.3
Local ECG					X				X							8.2.4
Adverse events	X	X	X	X	X	X	X	X	X							8.3, Appendix B
Concomitant medications	X	X	X	X	X	X	X	X	X							6.5
HRU Assessment																
HRU	X	X	X	X	X	X	X	X	X	X	X	X	X	X	X	8.10
Assess asthma exacerbations	X	X	X	X	X	X	X	X	X							8.1.1.6
Nasal polyps Assessments																
Nasal endoscopy			X	X	X	X				X				X		8.1.2
Sinus CT- scan														X ^{b)}		8.1.3
Assess nasal surgery or/and SCS use	X	X	X	X	X	X	X	X	X	X	X	X	X	X	X	8.1.4, 8.1.5, 6.5
Laboratory Assessments																
Clinical chemistry	X ⁱ⁾				X									X		8.2.1
Haematology	X ⁱ⁾			X	X					X				X		8.2.1
Urine pregnancy test, dipstick ⁱ⁾	X	X	X	X	X	X	X	X	X	X	X	X	X	X	X	5.1, 8.2.1.1
CCI	X															8.2.1.3
CCI	X															8.2.1.3

Study period	Treatment										EoDB ^{b)} /IPD ^{c)}	UNS ^{d)}	Refer to section	
	V3	V4	V5	V6	V7	V8	V9	V10	V11 ^{e)}					
Visit														
Week	w0	w4	w8	w16	w24	w32	w40	w48	w56					
Visit window (days) ^{a)}	±0	±3	±3	±7	±7	±7	±7	±7	±7					
PK ^{j)}	X			X	X		X		X					8.5
Immunogenicity ^{j)}	X			X	X		X		X					8.6
Exploratory biomarkers - blood for serum proteins ^{k)}	X				X				X ^{l)}					8.9
Exploratory biomarkers - blood for plasma proteins ^{k)}	X				X				X ^{l)}					8.9
Exploratory biomarkers - blood for transcriptomic profiling ^{k)}	X				X				X ^{l)}					8.9
Exploratory biomarkers - nasal secretion ^{k)}	X				X				X ^{l)}					8.9
CC1	X				X				X ^{l)}					8.9
DNA sample (optional) ^{k)}	X ⁿ⁾													8.8
Randomisation, Investigational Product Administration														
Randomization ^{e)}	X													4.1
Investigational Product dispensed and administration ^{p)}	X	X	X	X	X	X	X	X	X ^{q)}					6.1, 6.2
Other														
INCS distribution and accountability	X		X	X	X	X	X	X	X	X	X	X	X	6.5.1

- a. All visits to be scheduled from the date of randomization, not from the date of previous visit, except for early discontinuation from IP.
- b. For patients who will not enter the OLE, V11 will be EoDB.
- c. For patients who prematurely discontinue IP should return to the study site and complete the procedures described within 8 weeks after the last dose of IP.
- d. Unscheduled visits may be initiated as needed, and additional assessments may be performed at these visits as indicated.

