- e. Visit 11 is the last double-blind visit and the first OLE visit. Only patients who enter OLE will receive IP (first dose of open-label Benralizumab) at this visit. All assessments at Visit 11 to be performed before administration of open-label benralizumab.
- f. Patients to complete available assessments in-clinic prior to other study procedures.

- g. UPSIT smell test will be performed in all countries which have validated version of the test.
- h. Assessed at EoDB. For IPD patients only do assessment if at least 16 weeks since the previous CT scan. In case of surgery during the double-blind part of the study, the CT scan should be done prior to surgery instead of at week 56.
- i. Results will only be used as baseline data. Will not be used for eligibility check.
- j. At dosing visits, must be collected pre-dose.
- k. Additional exploratory biomarker samples (excluding CCI and DNA sample (optional) will be collected in all participating countries except for China Mainland. DNA sample will not be collected in China Taiwan.
- l. Assessed at EoDB. For IPD patients only do assessment if the time period between randomization and IPD visit is ≥ 24 weeks.
- m. CCI is the only exploratory biomarker collected in China Mainland.
- n. Samples can be collected at any time from Week 0 (V3) after genetic consent is signed.
- o. All V3 procedures and assessments must be performed prior to randomization/IP dosing.
- p. IP administration should be the last activity of the visit. All visit procedures should be done prior to dosing.
- q. IP administration will be applied to patients who enter the OLE.

ACQ-6- Asthma Control Questionnaire-6; CRSwNP- Chronic rhinosinusitis with nasal polyps; CT- Computed tomography; CCI ; EoDB- End of double-blind; HRU- Healthcare resource utilization; CCI IPD- Investigational product discontinuation; PGI-C- Patient Global Impression of Change; PGI-S- Patient Global Impression of Severity; PK- Pharmacokinetics; PRO- Patient -reported outcome; SCS- Systemic corticosteroids; SF-36v2- Short Form 36-item Health Survey, Version 2; SNOT-22- SinoNasal Outcome Test, 22 item; UNS- Unscheduled; UPSIT- University of Pennsylvania Smell Identification Test.

Table 3 Schedule of Activities – For the Open-label Extension and Follow-up

Study period	Open-label treatment period								FU/IPD ^{e)}	UNS ^{d)}	Refer to section
	V12	V13 ^{b)}	V14 ^{b)}	V15	V16 ^{b)}	V17 ^{b)}	V18 ^{b)}	V19			
Visit	W60	W64	W72	W80	W88	W96	W104	W112			
Week											

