4. STUDY DESIGN

4.1. Overall design

This is a randomised, double-blind, placebo-controlled, parallel-group, multicentre, Phase 3 study to evaluate the efficacy and safety of repeat dosing of benralizumab 30 mg administered SC versus placebo in patients with severe eosinophilic CRSwNP. Following completion of the double-blind period, patients have the option to enter an OLE.

Approximately 250 patients will be randomised, to receive benralizumab 30 mg SC or matching placebo.

Patients will be stratified by region and baseline CCI. Randomisation will be monitored to ensure that no more than CCI of the study population will have CCI. When the target percentage of patients in a subgroup is reached, consideration will be given to closing the IWRS randomisation for that subgroup. Once a subgroup is closed, patients in the screening/run-in period in the closed subgroup will not be allowed to be randomised and will be screen failed.

After enrolment, and prior to entering the screening/run in period, eligible participants will have their current INCS therapy switched to MFNS (400 mcg daily) or equivalent (highest local approved for CRSwNP), which should be maintained throughout the study until the last DB visit (V11). Patients must have been on a stable daily dose of INCS for at least 4 weeks prior to V1. Patients will be provided with an electronic patient-reported outcome (ePRO) device to record symptoms throughout the study until V11 (week 56) (see section 8.1.1 Clinical outcome assessments).

Patients who continue to meet eligibility criteria will be randomised 1:1 at Visit 3 (Day 0) to receive either placebo or benralizumab 30 mg SC every 4 weeks for the first 3 doses (Weeks 0, 4 and 8) and every 8 weeks thereafter (Weeks 16, 24, 32, 40 and 48). All patients who complete the 56-week DB treatment period on IP may be eligible to continue into an OLE, during which all patients will receive 8 doses of benralizumab 30 mg every QW4 for the first 3 doses (Weeks 56, 60, 64) and Q8W thereafter (Weeks 72, 80, 88, 96 and 104). Patients randomized to the Benralizumab arm during DB period will receive one dose of placebo (dummy) injection at Visit 12 (week 60) in order to maintain the blind.

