8.1.1.1. Nasal Polyps Symptom Diary

The patient will complete a 11-item NP Symptom Diary (NPSD) each morning throughout the screening, treatment and follow-up periods. The patient is asked to consider their experience with NP over the past 24 hours when responding to each question. Patients are asked to report their experience with NP symptoms (nasal blockage, nasal congestion, runny nose, postnasal drip (mucus drainage down the throat), headache, facial pain, facial pressure, and difficulty with sense of smell) and symptom impacts (difficulty with sleeping due to nasal symptoms and difficulty with daily activities due to nasal symptoms). Patients report the severity of each symptom and symptom impact at its worst using a 4-point verbal rating scale (0-None to 3-Severe). A Total Symptom Score (TSS) is calculated by taking the sum of the 8 equally weighted symptom items. A single item to capture INCS or LTRA compliance (yes or no) will be administered after the symptom and symptom impact items.

A 2-week recall version of the diary (Nasal Polyps Symptom Screening Assessment) will be used to evaluate minimum symptom criteria at Visit 1. This screening assessment has one additional item about consistency of symptoms over the past 12 weeks and omits the medication compliance item; otherwise concepts measured are the same as the NPSD.

The NPSD will be completed on the ePRO device per the SoA.

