1.3 Study design

This is a randomised, double-blind, placebo-controlled, parallel-group, multicentre, Phase 3 study to evaluate the efficacy and safety of repeat dosing of benralizumab 30 mg administered subcutaneously (SC) versus placebo in patients with severe CRSwNP. Following completion of the double-blind period, patients have the option to enter an OLE.

Approximately 250 patients will be randomised to receive benralizumab 30 mg SC or matching placebo.

Patients will be stratified by region **CCI**

CCI

After enrolment, and prior to screening/run in period (at V1), eligible patients will have their current INCS therapy switched to Mometasone Furoate (400 ug daily) or equivalent (highest local approved for CRSwNP), which should be maintained throughout the study until the last DB visit (V11). Patients must have been on a stable daily dose of INCS for at least 4 weeks prior to V1. Patients will be provided with an electronic patient-reported outcome (ePRO)

device to record symptoms and health-related quality of life (HRQL) data throughout the study until V11 (Week 56).

Patients who continue to meet eligibility criteria will be randomised 1:1 at Visit (V) 3 (Week 0) to receive either placebo or benralizumab 30 mg SC every 4 weeks for the first 3 doses (Weeks 0, 4 and 8) and every 8 weeks (Q8W) thereafter (Weeks 16, 24, 32, 40 and 48). All patients who complete the 56-week DB treatment period on investigational product (IP) may be eligible to continue into an OLE, during which all patients will receive 8 doses of investigational product, every Q4W for the first 3 doses (Weeks 56, 60, 64) and Q8W thereafter (Weeks 72, 80, 88, 96 and 104). Patients randomised to the benralizumab arm during DB period will receive one dose of placebo (dummy) injection at Visit 12 (week 60) in order to not get a loading dose again and to maintain the blind.

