3. PRIMARY AND SECONDARY VARIABLES

3.1 General principles

3.1.1 Study periods for data summary

The following study periods will be derived for reporting purposes:

- Double-blind period: this is defined as the period starting on the date of randomization (for efficacy) or date of first dose of study treatment (for safety), and ending on the date of first OLE dose (for those who entered the OLE right after DB completion), or the date of the Week 56 Visit (for those who did not enter the OLE after DB, or those who entered the DB follow-up period per CSP v1.0 and v2.0). For patients who discontinued the study before the Week 56 Visit, the DB period ends on the last participation date.
 - Specifically, patients who enter the OLE period will receive their first OLE dose at the Week 56 Visit, after completion of all visit-related assessments. Therefore, all assessments at the Week 56 Visit are counted under the DB

period, and the first OLE dose (i.e. last procedure at the visit) indicates the start of the OLE period.

- Extended follow-up period, off treatment (applicable to CSP v1.0 or v2.0):
 - for patients who did not enter the OLE: this is defined as the period starting on the date after the end of DB period and ending on the date of last participation in the study.
 - for patients who were followed up off-treatment after DB period and then entered the OLE: this is defined as the period starting on the date after the end of DB period and ending on the date of first OLE dose.
- Open-label period: this is defined as the period starting on the date of first OLE dose and ending on the date of last participation in the study.
- On-study period: this is defined as the period starting on the date of randomization (for efficacy) or date of first dose of study treatment (for safety) and ending on the date of last participation in the study.

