For assignment of data to adjusted analysis-defined visit windows, study day will be calculated relative to the reference start date, which is the date of randomization for efficacy variables and the date of first dose of study treatment for safety variables.

- Screening period: $Study\ day = Date\ of\ assessment - reference\ start\ date$
- After randomisation: $Study\ day = (Date\ of\ assessment - reference\ start\ date) + 1$

The adjusted analysis-defined windows for NPS are defined as in [Table 3](#) below:

Table 3 Adjusted analysis-defined visit windows for NPS

Analysis-defined visit windows	Scheduled study day	Maximum windows
Week -6	-42	$-49 \leq Study\ day \leq -15$
Week -2	-14	$-14 \leq Study\ day \leq 1$
Week 8	57	$2 \leq Study\ day \leq 84$
Week 16	113	$85 \leq Study\ day \leq 140$
Week 24	169	$141 \leq Study\ day \leq 224$
Week 40	281	$225 \leq Study\ day \leq 336$
Week 56	393	$337 \leq Study\ day \leq \min(434, \text{first OLE dose})$; first OLE dose is applicable for those who entered the OLE after DB completion

The NBS, DSS, Total Symptom Score (TSS), and other items in the nasal symptom scores diary (NPSD) will be summarised every two weeks (bi-weekly) and the adjusted windows are defined as in [Table 4](#) below.

Table 4 Adjusted analysis-defined visit windows for NPSD (including NBS, DSS, and TSS)

Analysis-defined visit windows	Scheduled study day	Maximum windows
Week 1, Day 1	1	$-13 \leq Study\ day \leq 1$
Week 2	15	$2 \leq Study\ day \leq 15$
Week 4	29	$16 \leq Study\ day \leq 29$
Week 6	43	$30 \leq Study\ day \leq 43$

...
Week 56	393	$380 \leq \text{Study day} \leq \min(393, \text{first OLE dose})$; first OLE dose is applicable for those who entered the OLE after DB completion

The general adjusted analysis-defined windows for the visits following baseline for all other assessments in Table 2 and Table 3 of the CSP is summarised in Table 5. The windowing will only be performed for assessments within the appropriate periods, e.g. double-blind versus open label.

Table 5 General analysis-defined visit windows for assessments

Analysis-defined visit windows	Scheduled study day	Maximum windows
Week 1 Day 1	1	Study day=1
Week X	$X*7+1=a$	$2 \leq \text{Study day} \leq ((b-a)/2+a)-1$
Week Y ^a	$Y*7+1=b$	$((b-a)/2+a) \leq \text{Study day} \leq ((c-b)/2+b)-1$
Week Z	$Z*7+1=c$	$((c-b)/2+b) \leq \text{Study day}$

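### The Week 56 diary window starts on a fixed Day 380 but can close early at V11, so some protocol-compliant early attenders lose an observed Week 56 NBS and DSS

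*SAP*

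**What the plan says.** - **Window.** SAP section 3.1.2 introduces Table 4 for the diary items with the words "NPSD) will be summarised every two weeks (bi-weekly) and the adjusted windows are defined as in" that table. Table 4 places Week 56 at Day 393 and accepts diary days from 380 to the smaller of 393 and the first OLE dose. Its note reads "first OLE dose is applicable for those who entered the OLE after DB completion". Week 54, by the same two-week pattern, is Days 366-379.
- **When the window can close.** SAP section 3.1.1: "patients who enter the OLE period will receive their first OLE dose at the Week 56 Visit". Protocol Table 2, footnote e: "Visit 11 is the last double-blind visit and the first OLE visit". The same table gives V11 a window of ±7 days, and footnote a reads "All visits to be scheduled from the date of randomization, not from the date of previous visit".
- **When the diary stops.** Protocol section 4.1 provides a "device to record symptoms throughout the study until V11 (week 56"); SAP section 1.3 says much the same. Protocol section 8.1.1.1 is wider, with diary entries "each morning throughout the screening, treatment and follow-up periods".
- **Minimum data.** SAP sections 3.3.2 (NBS) and 3.4.1 (DSS) require 8 evaluable days in each 14-day period; otherwise the mean is missing.
- **Consequences.** Under SAP section 4.2.5.1 a non-rescued patient's missing value is multiply imputed. Under section 4.2.5.4 a patient with no evaluable Week 56 value counts as a non-responder.

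**The concern.** The end of the Week 56 window adapts to an early V11, but the start does not, and the 8-day minimum is not scaled. A patient who attends within the permitted visit window can therefore have too few countable days. The entries from the days just before Day 380 exist but are assigned only to Week 54. No passage in either document moves the window back.

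The other co-primary endpoint does not have this problem. The Week 56 window for NPS opens on Day 337, so the same early visit keeps its endoscopy score while possibly losing its diary score. At stake are observed values of a co-primary endpoint (NBS) and of the first key secondary endpoint (DSS).

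**Working it through.** **Plan's own figures first.** Randomisation is Day 1, so Week 56 = 56 × 7 + 1 = Day 393, and 393 − 380 + 1 = 14 days. Both agree with Table 4. For power (SAP section 1.4), a two-sided t-test with 125 per arm gives 91.7% for NPS (0.85, SD 2) and 88.3% for NBS (0.4, SD 1). The product, treating the two as independent, is 81.0%, consistent with the stated overall 80%.

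**Diary days available.** V11 is permitted on 393 ± 7 = Days 386-400. With the diary ending at V11, days in the window are L = min(393, V11 day) − 380 + 1, and L − 8 missed entries can be tolerated.

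**Chance of no Week 56 mean.** Daily completion p is not in the documents; I assume 90% or 80%, independent between days. Protocol section 8.1.1 has an uncompleted at-home assessment done at the site before other procedures, so I treat the V11-day entry as secured. The chance is then 1 if L < 8, otherwise P(Bin(L − 1, p) ≤ 6). For V11 after Day 393 the secured entry lies outside the window and the chance is P(Bin(14, p) ≤ 7).

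| V11 day | Days in window | Misses tolerated | No mean, p = 90% | No mean, p = 80% |
|---|---|---|---|---|
| 386 | 7 | none possible | 100% | 100% |
| 387 | 8 | 0 | 52.2% | 79.0% |
| 388 | 9 | 1 | 18.7% | 49.7% |
| 389 | 10 | 2 | 5.3% | 26.2% |
| 390 | 11 | 3 | 1.3% | 12.1% |
| 391 | 12 | 4 | 0.3% | 5.0% |
| 392 | 13 | 5 | 0.05% | 1.9% |
| 393 | 14 | 6 | 0.01% | 0.7% |
| 394-400 | 14 | 6 | 0.02% | 1.2% |

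**Averaging over V11 days.** V11 timing is not documented either. I use three patterns over Days 386-400: tightly clustered (normal, SD 2 days around Day 393), triangular (weight (8 − |day − 393|)/64) and uniform (1/15 each). The Day 386 share, where loss is certain, is 0.04%, 1.6% and 6.7%. Let f be the overall share without a Week 56 mean.

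**Precision and power.** I approximate information lost after imputation as f × (1 − ρ²), with the Week 54-56 correlation ρ assumed to be 0.9 to 0.7. NBS power uses 125 × (1 − loss) per arm; NPS power stays at 91.7%.

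| p | V11 pattern | f | Information lost | Joint power |
|---|---|---|---|---|
| 90% | tight | 0.6% | 0.11-0.31% | 80.9-81.0% |
| 90% | triangular | 4.5% | 0.86-2.32% | 80.3-80.7% |
| 90% | uniform | 11.9% | 2.25-6.05% | 79.1-80.3% |
| 80% | tight | 3.7% | 0.70-1.89% | 80.4-80.8% |
| 80% | triangular | 10.2% | 1.94-5.21% | 79.4-80.4% |
| 80% | uniform | 18.9% | 3.58-9.61% | 77.9-79.9% |

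With 14 days ending at V11 for early attenders, joint power under the same assumptions is 81.0% at 90% completion and about 80.9% at 80%.

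**Supportive NBS responder analysis.** Scoring these patients as non-responders multiplies each arm's rate by (1 − f). Illustrative true rates of 50% and 30% give an odds ratio of 2.33. In the uniform case at 90%, the rates become 0.5 × 0.881 = 0.441 and 0.3 × 0.881 = 0.264, and the odds ratio is (0.441/0.559)/(0.264/0.736) = 2.19. At 80%, the multiplier is 0.811 and the odds ratio is 2.12.

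**The case against.** The strongest reply is that the plan already absorbs the consequence. Non-rescued completers remain in the ANCOVA, the earlier diary entries still feed Week 54, and Week 54 informs the imputation. Fixed, non-overlapping windows with multiple imputation are a coherent design. This stands as a limit on the size of the problem. It does not explain why a collected value should be imputed.

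The magnitudes also rest on undocumented assumptions. The power calculation credits the imputation with Week 54 only, whereas it uses the whole prior diary series. With an exchangeable correlation of 0.7 and seven earlier windows, R² is 7 × 0.49/(1 + 6 × 0.7) = 0.66 rather than 0.49, cutting the loss by about a third. Under a first-order autoregressive pattern there is no such gain. The low ends are therefore worst cases.

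Scope is narrower than all early attenders. The cut at the first OLE dose applies only to OLE entrants. For others the loss depends on when the diary stops: Protocol section 7.1.1 lets patients who discontinued treatment keep the device until the end of the double-blind period, and section 8.1.1.1 mentions diary use in follow-up.

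A reader might infer that early attenders are dropped, that every one of them loses the endpoint, or that the treatment comparison is biased. The documents do not support this. The analysis set is unchanged, loss is certain only on Day 386, and nothing links V11 timing or diary completion to treatment arm. No type I error effect is shown either.

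Finally, the remedy shares days between Week 54 and Week 56 and changes some means that are already evaluable. Those costs are real but small.

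**Conclusion.** The day arithmetic is certain: a V11 on Day 386 complies with the protocol, yet no observed Week 56 NBS or DSS can result, and a V11 on Day 387 tolerates no missed entry. The consequence for the primary NBS and DSS analyses is a small, avoidable loss of precision.

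Its size cannot be settled from the documents, because it depends on V11 timing, daily completion and correlation between diary periods, all assumed here. With tight clustering and 90% completion it is negligible. The largest loss, about 3 points of joint power (81.0% to 77.9%), needs uniform V11 timing, 80% completion and a correlation of 0.7 together.

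The pull of the NBS responder odds ratio towards 1 is slight and lies outside the testing hierarchy; DSS has no responder analysis. This is a cheap improvement, not a threat to the trial's conclusions.

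**What to change.** Before unblinding, amend the Week 56 row of SAP Table 4:

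1. For non-rescued patients whose V11 or first OLE dose falls on Days 386-392 and whose diary ends there, define the Week 56 window as the 14 days ending on that date.
2. Keep the 8-day minimum. Apply the rule to all diary items (NBS, DSS, TSS and the others) and to every such early attender, whether or not the current window is evaluable, so that the window does not depend on how complete the diary is.
3. Otherwise keep the current window, including for patients who keep the device beyond V11 and for V11 before Day 386. Without that lower limit, a V11 on Day 375 would label Days 362-375 as Week 56.
4. Leave Week 54 at Days 366-379, and name the overlap as an exception to the one-visit allocation in section 3.1.2.
5. Keep the section 4.2.5.1 handling for rescued patients, so that a worst-possible or worst-observed value is not replaced by a pre-rescue mean.

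The cost is a few lines of text and a small programming change, with no new data. For early attenders, between 1 day (V11 on Day 392) and 7 days (Day 386: window 373-386 against Week 54 ending on Day 379) count in both periods, so the two variables share data in the imputation model. Their already evaluable Week 56 means change slightly.
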